## 1.0 Purpose of the study:

Charles River Analytics and our collaborators at The New England Consortium propose to develop and evaluate an Immersive Modular Preparedness Intelligent Tutor (IMPRINT). IMPRINT aims to enhance trainee performance and set operational expectations outside of the hot zone in hyper-realistic exercises that challenge physical, psychological, and cognitive capabilities through adaptive behavioral science enhanced virtual reality (VR) modules and seamlessly integrate with HAZWOPER training. The overall objective of IMPRINT Phase II is to conduct a 1-year randomized-controlled trial among regular HAZWOPER Trainees comparing protocol adherence during required hands-on field exercises for trainees who used the IMPRINT behavioral science VR training with trainees who received standard PowerPoint and video training.

We anticipate trainees and classes assigned to the intervention will perform better than those who use standard paper and PowerPoint based activities. We believe their comprehension of topics will be greater, and it is likely that they will have a greater ability to recall HAZWOPER guidelines in the field. We also anticipate after class survey results will indicate a better HAZWOPER training experience and increased levels of satisfaction with the course.

Additionally, we anticipate that trainers using the IMPRINT VR modules will find the tool more effective and engaging compared to standard PowerPoint and video-based training methods. We expect that trainers will report greater ease in delivering complex HAZWOPER concepts and that the VR modules will enhance their ability to facilitate trainee comprehension and recall of HAZWOPER guidelines. We also anticipate that trainer feedback will reflect a more positive teaching experience and higher levels of satisfaction with the training process.

Long-term benefits of participation include improvement in retention of HAZWOPER guidelines when responding to Hazardous Material (HAZMAT) disasters. We anticipate trainees and classes assigned to the intervention will perform better than those who use standard paper and PowerPoint based activities. We believe their comprehension of topics will be greater, and it is likely that they will have a greater ability to recall HAZWOPER guidelines in the field. We also anticipate after class survey results will indicate a better HAZWOPER training experience and increased levels of satisfaction with the course.

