## 4.0 Sample Size:

According to The New England Consortium, during the pandemic they have trained approximately 15-25 people per class once a month.

Our study follows two stages. First, we will conduct a Pilot consisting of 2 months with one month serving as a case and the other month serving as the control. The Pilot will be used to indicate effect size. (30-50 participants)

Our study will also include the main evaluation, consisting of 6 randomly selected courses that receive the IMPRINT VR intervention and 6 randomly selected control courses. (180-300 participants)

This creates a sample of approximately 300 participants.

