## **8.0 Procedures Involved:**

The standard TNEC 40-hour workbook will be used in both the intervention and control classes.

In the intervention, trainees will be provided with an Oculus VR headset to complete virtual reality modules based on activities covered in the TNEC 40 hour course workbook. In control classes, trainees will complete all of the activities following standard practice which includes filling out sheets, reviewing 2D photographs, and reviewing slides. VR modules will last no longer than 1-5 minutes in length, which is a comparable length to the time allowed for students in control classes to complete their assigned tasks. There will be no differences in content provided between cases and controls. We are examining the effect of a difference in delivery mechanism and interaction with the content to enhance retention, understanding, and performance.

VR modules will be provided intermittently throughout the 40 hour course. Each course is required to be 40 hours in length by the OSHA standard.

All evaluations and assessments of trainees will take place at the same sequence between cases and controls.

Outcomes measured include student accuracy on the TNEC HAZWOPER performance instruments including; 1) the 40 Hr HazWoper Course Workbook, 2) the Toxic Properties Activity, 3) The New England Consortium Health and Safety Training Survey, 4) System Usability Scale (SUS), 5) Occupational Self-

Efficacy Scale - Short Form (OSS-6), 6) iGroup Presence Questionnaire (IPQ), 7) Flow State Scale (FSS), 8) UX for VR Questionnaire, and 9) NASA-TLX

We will first run a two-month pilot to estimate ICC, the intraclass correlation coefficient. We will use ICC to determine effect size for the following 12-month study (see Figure 10). Using this calculation, we will determine expected effect size from the more extensive 12-month portion of the evaluation effort.

Prior to analysis of the 12-month effort, we will use matching techniques based on trainee and trainer characteristics. We will use pretest matching criteria based on trainee cohort population characteristics and prior knowledge ascertained through pre-HAZWOPER training registration information.

[figure not shown]
[figure not shown]

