We will match cases and controls using Euclidian distance between intervention and control samples rather than propensity score matching to find the best match to mitigate risk of confounding due to low sample size following the guidance of [name] (King, G. and Nielsen, R., 2019. Why propensity scores should not be used for matching. *Political Analysis*, 27(4), pp.435-454.). We will compare how these modules enhance student performance across TNEC HAZWOPER performance instruments including; 1) the 40 Hour HAZWOPER Course Workbook, 2) the Toxic Properties Activity, 3) The New England Consortium Health and Safety Training Survey, 4) System Usability Scale (SUS), 5) Occupational Self-Efficacy Scale - Short Form (OSS-6), 6) iGroup Presence Questionnaire (IPQ), 7) Flow State Scale (FSS), 8) UX for VR Questionnaire, and 9) NASA-TLX

We will compare how these modules enhance performance through a t-test.

[figure not shown]
Intervention VR modules will be based on the existing activities within the 40 Hour HAZWOPER Course Workbook and the field exercise including:

Module 1 Duration: 5 Minutes	Activity 3-A What's on the Site?
------------------------------------	----------------------------------

[figure not shown]
Instrument	
3.1 CHEMICAL HAZARDS - 3 • Pg 4
 
ACTIVITY3-A
 
WHAT'S ON THE SITE?
 
Purpose: To start developing a list of clues that can be used to decide if hazardous chemicals are present on site. To get you thinking about what you need to know in order to work safely on site. To stress the importance of information and knowing where to get it.
 
Task: As a group, answer questions 1-3 using the following information: the site description below, the site map on pg. 5, and the photographs in your site packet. Numbers on the site map correspond to photo numbers. The arrows indicate the direction from which the photo was taken.
 
Site Description: Bright Corporation was a small metal plating company located on a 2 acre site. It operated between 1955 and 1992. The company was engaged in plating and painting of small metal parts. A lead acid battery manufacturer occupied the site between 1992 and 1995. The site has been abandoned for six months.
 
 
1. What clues suggest that chemical hazards may be present?
 
2. What else would you like to know about this site before entering?
 
3. Where would you go for this information?
 

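### Euclidean matching of the arms followed by a t-test either leaves the estimate as it was or changes it only by dropping or reweighting trainees; a baseline-adjusted course-level comparison keeps everyone and deals with measured imbalance directly

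*Combined protocol and SAP*

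**What the plan says.** Section 1.0 states the aim to "conduct a 1-year randomized-controlled trial among regular HAZWOPER Trainees". Section 4.0 gives the main evaluation as "6 randomly selected courses that receive the IMPRINT VR intervention and 6 randomly selected control courses", so the course is the unit of allocation.

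The analysis is in section 8.0. The timing is: "Prior to analysis of the 12-month effort, we will use matching techniques based on trainee and trainer characteristics". The variables are "pretest matching criteria based on trainee cohort population characteristics and prior knowledge ascertained through pre-HAZWOPER training registration information". The method is: "We will match cases and controls using Euclidian distance between intervention and control samples rather than propensity score matching". The reason given is "to find the best match to mitigate risk of confounding due to low sample size". The comparison is one sentence: "We will compare how these modules enhance performance through a t-test".

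The readable text does not state whether trainees or courses are matched, the ratio, any cut-off on distance, whether controls can be reused, what happens to unmatched trainees, or whether the t-test is paired. It plans no covariate adjustment and no course-level model, although section 8.0 also says "We will first run a two-month pilot to estimate ICC, the intraclass correlation coefficient".

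**The concern.** With only 12 courses, chance imbalance between the arms is likely, so the sponsor has good reason to account for baseline. Other features could add imbalance. Trainees choose their own course (section 3.0). A virtual-reality phrase is added to the course title, without saying whether control courses carry it (section 5.0). Contracted offsite classes are included (section 6.0).

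The question is whether matching followed by a plain t-test does this job. An unweighted t-test uses the matching only through which units remain and, if paired, through its standard error. Matching that keeps every unit cannot move the estimate. Matching that does move it gives up part of the randomised comparison. At stake is either an imbalance left in place in a result presented as matched, or trainees discarded by a rule that the plan does not state.

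**Working it through.** **Inputs from the documents.** 6 v 6 courses of 15–25 trainees (section 4.0): 12 × 15 = 180 and 12 × 25 = 300, which reproduces the stated 180–300. No alpha, power, effect size, SD, ICC value, baseline correlation or cut-off is given.

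**Assumptions.** Two-sided 5%, 80% power, total variance 1, mean course size 20, ICC 0.05 (also 0.10), two baseline covariates varying within course with R² 0.30 (range 0–0.50), and prior knowledge 0.25 SD higher in one arm (range 0.1–0.5).

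**1. All units kept.** If each unit in each arm is used exactly once, the mean of the pair differences equals the difference in arm means. Six course pairs therefore give the unmatched estimate, and none of any gap is removed. Pairing changes only the standard error and the degrees of freedom.

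- Detectable difference on 10 df: SE = √[(2/6)(ICC + (1 − ICC)/20)] = √[(1/3)(0.05 + 0.0475)] = 0.180. Multiplying by (t₀.₉₇₅ + t₀.₈₀) = 3.107 gives 0.560 SD.
- Six pairs, 5 df: the multiplier rises by 1.123, so the detectable difference is 0.560 × 1.123 = 0.629 SD if pairing adds no correlation.
- Break-even within-pair correlation: 1 − 1/1.123² = 0.21.

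**2. Trainees matched.** With R² split equally over two covariates, each slope is √0.15 = 0.387, so a 0.25 SD gap creates a false effect of 0.25 × 0.387 = 0.097 SD. The table shows simulation results (800 to 4,000 trials per setting) for optimal 1:1 matching on standardised covariates at ICC 0.05. Each standard error is set against the adjusted analysis in the same run.

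| Cut-off | Trainees dropped | False effect left | SE, matched v adjusted |
|---|---|---|---|
| None | about 4% | about two-thirds (0.069 of 0.097; 0.064 of 0.094) | 0.174 v 0.166 (no gap) |
| 0.75 SD | about 7% | about half | 0.175 v 0.166 |
| 0.5 SD | about 14% | 20–30% (0.02 of 0.094; 0.028 of 0.104) | 0.175 v 0.167 |
| 0.25 SD | about 40% | nearly none | 0.187 v 0.164 |

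The 4% comes from unequal arm sizes alone. The loss at a tight cut-off depends on how it is applied: discarding pairs wider than 0.25 SD after optimal matching dropped 56%.

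**3. Trainee-level adjustment.** Slopes are estimated within courses, then adjusted course means are compared.

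- False effect left: about 0.00 if baseline is measured without error. With measurement error, the share left is roughly 1 − reliability. At reliability 0.7 that is 0.3 × 0.097 = 0.03; at 0.5 it is 0.5 × 0.097 = 0.05. About a third to a half therefore remains.
- SE against matching without a cut-off, ICC 0.05: R² 0, 0.1824 v 0.1843 (1% lower); R² 0.10, 0.1773 v 0.1813 (2%); R² 0.30, 0.1656 v 0.1739 (5%); R² 0.50, 0.1573 v 0.1720 (9%). At ICC 0.10 and R² 0.30: 0.2105 v 0.2187 (4%).
- Detectable difference against the unadjusted course-level test: √[(1/3)(0.05 + 0.65/20)] × 3.107 = 0.515, down from 0.560 SD. At ICC 0.10 it is 0.647, down from 0.683.

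**4. Adjusting course means instead.** Regressing the 12 course means on two covariates gave SE 0.1867, worse than no adjustment (0.1810).

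**The case against.** **Matching may be of courses.** Section 8.0 names trainer and cohort characteristics, which belong to courses, and the figures that might show the unit and form of the test are not readable. If courses are paired, nobody is dropped and a paired test is already course-level inference. This stands: the table in step 2 would not apply, and what remains is an unadjusted estimate and 5 df. Even the loss of df disappears if pairing achieves a correlation above 0.21. Pairing before allocation would answer the point altogether, but matching done ahead of analysis, between intervention and control samples, does not read that way.

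**Matching is not all or nothing.** A reader might infer that the plan must either adjust nothing or discard a large share of trainees. That is too strong: a 0.5 SD cut-off removes most of the assumed gap for about 14% of trainees, and matching with replacement or 1:many would reweight rather than drop. The documents specify none of these.

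**Self-selection by arm is not shown.** A reader might infer that the arms are confounded. Section 3.0 describes self-selection into the training, not into an arm, and section 5.0 does not say which courses carry the added title wording. The 0.25 SD gap is only an illustration.

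**Adjustment needs data that may not exist.** Section 8.0 takes prior knowledge from registration but describes no test score and does not say that it is held per trainee. Activities 3-A and 3-B in the same section are at least partly group work, so individual scores may be lacking for them. Both limits stand and shape the fix.

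**The precision gain is small.** Agreed. The main argument is handling measured imbalance without losing trainees. The inflated type I error of a trainee-level t-test that ignores courses is a separate matter and is not counted here.

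**Conclusion.** The concern holds in a limited form. As written, matching then a t-test either leaves the estimate unchanged (1:1, all units kept) or changes it only by dropping or reweighting trainees, to a degree set by a cut-off that the plan does not give. Under the stated assumptions, the false effect left runs from about two-thirds with 4% dropped to almost none with about 40% dropped. Trainee-level adjustment removes the measured gap with nobody dropped, leaves about a third to a half of it if baseline reliability is 0.7 to 0.5, and lowers the standard error by about 5% at R² 0.30 and about 1% at R² 0.

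The identity in step 1 needs no assumption. Every other figure rests on assumed ICC, R², gap and cut-off. The documents do not support saying that the arms are confounded, that trainees will certainly be discarded, or that adjustment would remove all bias.

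**What to change.** In section 8.0, name one primary analysis:

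- Include every consenting trainee with an outcome, in the arm of their course, and report numbers without an outcome by arm.
- Stage 1: adjust trainee outcomes for prior knowledge from registration and at most one or two other registration variables named before data are seen, with slopes estimated within courses.
- Stage 2: compare the 6 v 6 adjusted course means by t-test on 10 df.
- Apply stage 1 only to outcomes scored individually.
- If registration data exist only as course summaries, make the unadjusted course-mean t-test on 10 df primary, and do not regress 12 course means on several covariates.

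As sensitivity analyses only, use a mixed model with a random course effect and small-sample correction, and matching with unit, ratio, cut-off, scaling and form of test stated. Trainer characteristics, being course-level, also belong there. If courses are in fact paired before allocation, say so and analyse by pair.

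The cost is a change of analysis wording and a check that individual baseline and outcome records can be linked; no more courses or trainees are needed. The downsides are few covariates, one missing-value rule applied alike to both arms, no repair of unmeasured or poorly measured self-selection, and no precision gain if baseline is not prognostic.

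### Whole courses are allocated, 6 against 6, but the only stated test is a t-test with no unit; run on trainees, its type I error would be 13–19% at an assumed ICC of 0.05 (nominal two-sided 5%).

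*Combined protocol and SAP*

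**What the plan says.** Section 4.0 sets the main evaluation as "6 randomly selected courses that receive the IMPRINT VR intervention and 6 randomly selected control courses", with 15 to 25 people per class and 180 to 300 participants in all. Section 8.0 gives the analysis in one sentence: "We will compare how these modules enhance performance through a t-test". The readable text adds no unit of analysis, course-level summary, mixed model, cluster-robust error or degrees of freedom.

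The outcomes are described per student: "Outcomes measured include student accuracy on the TNEC HAZWOPER performance instruments", and later "We will compare how these modules enhance student performance across TNEC HAZWOPER performance instruments". Section 1.0, however, speaks of both trainees and classes being assigned to the intervention.

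The intraclass correlation appears once, in Section 8.0. It is to be estimated in the two-month pilot, and then: "We will use ICC to determine effect size for the following 12-month study (see Figure 10". That figure is not visible in the text reviewed. It is cited for the effect-size step, not for the test. The pilot has "one month serving as a case and the other month serving as the control" (Section 4.0).

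Matching comes before the comparison: "Prior to analysis of the 12-month effort, we will use matching techniques based on trainee and trainer characteristics". The method is stated as: "We will match cases and controls using Euclidian distance between intervention and control samples".

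**The concern.** Because whole courses are allocated, any influence shared by one course's trainees falls entirely in one arm. A t-test on the 12 course means takes that into account. A t-test on 180 to 300 trainees treats them as independent. If courses differ, its standard error is too small, and its critical value is about 1.97 when the design supports 2.228 (10 df). The sentence in Section 8.0 permits either test, and the per-student wording of the outcomes points to the invalid one.

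A positive ICC is plausible. Section 3.0 says trainers tailor each course to the people enrolled. Activities 3-A and 3-B in Section 8.0 are done as group work, which adds to the similarity of workbook scores, though not of the self-report scales.

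This is the only comparison method the plan names. If the unit stays open, it can be chosen after the outcomes are seen.

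**Working it through.** **1. The plan's own figure.** 12 × 15 = 180 and 12 × 25 = 300, which reproduces the range in Section 4.0. It is a headcount; the documents give no power calculation, significance level or ICC to reproduce.

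**2. Inputs.** From Section 4.0: 6 courses per arm and m = 15 to 25 trainees per course. Assumed, because the documents give none: two-sided 5% level, 80% power, outcome in SD units, and ICC 0.01, 0.05, 0.10 and 0.20 (the two higher values are illustrative).

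**3. Trainee-level t-test.** Design effect DE = 1 + (m − 1) × ICC. Standard errors are too small by √DE. Type I error = 2 × [1 − Φ(1.96/√DE)], and coverage of the nominal 95% interval is 1 minus that. At ICC 0.05:

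- m = 15: DE = 1 + 14 × 0.05 = 1.70, √DE = 1.304, type I error 13.3%
- m = 20: DE = 1 + 19 × 0.05 = 1.95, √DE = 1.396, type I error 16.0%
- m = 25: DE = 1 + 24 × 0.05 = 2.20, √DE = 1.483, type I error 18.6%

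The interval ratio compares a valid 10-df interval with the trainee-level one. The standard errors are √[2(ICC + (1 − ICC)/m)/6] and √[2/(6m)]. At m = 20 and ICC 0.05 the half-widths are 2.228 × √(2 × 0.0975/6) = 0.402 and 1.97 × √(2/120) = 0.254, a ratio of 1.58.

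| ICC | Type I error, m = 15 / 20 / 25 | SE too small by | Interval too narrow by | Actual coverage |
|---|---|---|---|---|
| 0.01 | 6.6 / 7.2 / 7.8% | 1.07–1.11 | 1.21–1.26 | 92–93% |
| 0.05 | 13.3 / 16.0 / 18.6% | 1.30–1.48 | 1.47–1.68 | 81–87% |
| 0.10 | 20.6 / 25.0 / 28.8% | 1.55–1.84 | 1.75–2.09 | 71–79% |
| 0.20 | 31.5 / 37.1 / 41.6% | 1.95–2.41 | 2.20–2.73 | 58–69% |

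The harm depends on the ICC. At 0.001 the error is only 5.2–5.3%. It reaches 10% when DE = (1.95996/1.64485)² = 1.4199, so ICC = 0.4199/(m − 1): 0.030 at m = 15 and 0.017 at m = 25.

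**4. Check by simulation.** With no true effect, ICC 0.05 and 40,000 runs per setting, the trainee t-test rejected in 13.1%, 16.3% and 18.7% of runs for m = 15, 20 and 25. The t-test on course means rejected in 5.0%, 5.0% and 5.2%. With course sizes varying from 15 to 25 (10,000 runs), rejection rates at the four ICC values were:

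- trainee t-test: 7.4%, 16.6%, 25.7%, 37.7%
- course means, 10 df: 5.2%, 5.0%, 5.3%, 4.7%
- paired course means, 5 df: 5.1%, 4.8%, 5.1%, 4.9%

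**5. Does matching trainees first remove the problem?** Simulated with 20 per course, matching on prior knowledge (assumed correlation 0.5 with outcome, caliper 0.1 SD), a course effect independent of the matching variable, and 5,000 runs. Type I error at the four ICC values:

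- paired t-test on matched trainees: 8.3%, 17.4%, 26.3%, 39.8%
- two-sample t-test on matched trainees: 5.4%, 12.7%, 20.9%, 34.2%
- course means: 4.9%, 4.9%, 4.6%, 4.4%

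If matching explains part of the course variation, the row for the lower residual ICC applies.

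**6. Can the pilot supply the ICC?** With one VR class and one control class, class variation and the VR effect are the same contrast. With no clustering at all, an effect of d SD gives a between-class variance of d²/2. For d = 0.3 that is 0.045, an apparent ICC of 0.045/1.045 = 0.04. For d = 0.5 it is 0.125, an apparent ICC of 0.125/1.125 = 0.11.

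**The case against.** The best defence is that the plan is silent rather than wrong. A t-test on course means fits its sentence, and some text leans that way: Section 1.0 names classes, and Section 8.0 matches on trainer and cohort characteristics and cites a low sample size, which suits 12 courses better than 180 to 300 trainees. The plan mentions the ICC, so clustering has not been overlooked. Figures that could not be seen might show the analysis structure. The size of the ICC is also unknown: Section 3.0 describes students from varied employers and backgrounds, and Section 8.0 keeps the workbook, content and assessment sequence the same across arms.

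Part of this stands. The inflated error belongs to one reading only, and its size rests on an assumed ICC and significance level. At ICC 0.01 a two-sample test on matched trainees is close to nominal (5.4%), so matching fails clearly only at larger ICCs, or when the matched test is paired (8.3% even at 0.01). Matching on trainer and cohort characteristics could also absorb some course variation.

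The rest does not answer the point. None of the passages that hint at classes states a unit. The ICC is tied to effect size, never to the test, and an ICC is not an effect size. Matching trainees does not remove an influence shared by a whole course. If course means were intended, saying so costs nothing.

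**Conclusion.** The concern holds, with high confidence, and must be fixed. The plan allocates courses and names a test that, on its most natural reading, ignores them. If run on trainees at a nominal two-sided 5% level, the type I error is 13–19% at an assumed ICC of 0.05, with 7–8% at 0.01 and 21–29% at 0.10. At ICC 0.05 the information is that of about 106 independent trainees out of 180 (180/1.70), or 136 out of 300 (300/2.20). If the test is run on course means, no inflation arises; the defect is that the readable text does not say so.

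**What to change.** Replace the t-test sentence in Section 8.0 with:

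> The course is the unit of allocation and of inference. Each instrument compared between arms is analysed by a two-sided t-test on the 6 VR and 6 control course means (10 df), or, if courses are matched in pairs, by a paired t-test on the 6 pair differences (5 df). The ICC from the main evaluation is reported with its confidence interval.

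State which of the two tests applies before any outcome data are seen. A linear mixed model with a random course effect and a small-sample correction such as Kenward-Roger, adjusted for prior knowledge from registration, is an acceptable alternative if named equally early. If trainees rather than courses are matched, keep the course effect in the model.

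The cost is a changed sentence and a course code on each de-identified record; Section 19.0 describes a participant identifier and does not mention a course code. No extra trainees, visits or assessments are needed.

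The downside is less apparent precision. At ICC 0.05 and 20 per course, the half-width is 0.40 SD (10 df), or 2.571 × 0.180 = 0.46 SD if courses are paired (5 df) and pairing removes no between-course variation, against 0.25 SD. The difference detectable with 80% power is 0.56 or 0.63 SD, against 0.36 SD. The smaller figures hold only if trainees within a course are independent.

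### Nine instruments, most of them self-report scales by name, are all treated as performance and compared by t-test with no stated control of error across them

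*Combined protocol and SAP*

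**What the plan says.** Section 8.0 (Procedures Involved) introduces the outcomes with "Outcomes measured include student accuracy on the TNEC HAZWOPER performance instruments including" and numbers nine: the 40-hour Course Workbook, the Toxic Properties Activity, the TNEC Health and Safety Training Survey, the System Usability Scale, the Occupational Self-Efficacy Scale short form, the iGroup Presence Questionnaire, the Flow State Scale, and finally "8) UX for VR Questionnaire, and 9) NASA-TLX".

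Later in the section the same nine return under "We will compare how these modules enhance student performance across TNEC HAZWOPER performance instruments including". After a description of matching, the comparison itself is one sentence: "We will compare how these modules enhance performance through a t-test".

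The available text gives no alpha, sidedness, primary outcome, composite, ordering of outcomes or adjustment for several tests. Section 1.0 (Purpose) states the trial's comparison differently, as "comparing protocol adherence during required hands-on field exercises for trainees who used the IMPRINT behavioral science VR training". That outcome is not among the nine, although Section 8.0 shows a field training exercise/evaluation as the instrument for Module 3.

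**The concern.** Two problems come from putting all nine under one label.

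The first is what a result may be used to claim. Items 4 to 9 are, by name, scales of usability, self-efficacy, presence, flow, VR user experience and workload. They do not yield accuracy. Under the Section 8.0 wording, a difference on any of them still counts towards enhanced performance. Trainees cannot be blinded: one arm wears a headset, the other fills out sheets and reviews slides. Section 5.0 also adds virtual reality to the advertised course title, which may raise expectations. Self-report scales are the outcomes most exposed to this.

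The second is the error rate. One claim that can be supported by any of several tests, with no error control, has a false-positive rate well above that of a single test. The hypothesis is directional ("We anticipate trainees and classes assigned to the intervention will perform better than those who use standard paper and PowerPoint based activities"), so the error that matters most is a false result in favour of VR.

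**Working it through.** **Inputs from the documents.** There are nine instruments (Section 8.0, listed twice). The method is a t-test (Section 8.0). The main evaluation is "consisting of 6 randomly selected courses that receive the IMPRINT VR intervention and 6 randomly selected control courses. (180-300 participants"); 12 courses of 15 to 25 trainees give 12 × 15 = 180 and 12 × 25 = 300, so the headcount reproduces. The headcount does not enter the error calculation. The plan states no error rate, so there is no figure of its own to reproduce.

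**Assumptions not in the documents.** One test per instrument; two-sided alpha of 0.05; each test at its nominal size; a common correlation ρ between test statistics, shown at 0 and 0.5. Because scales about the VR system may have no control-arm data, a six-test case is also shown. It drops three scales, taken here from their names as usability, presence and UX for VR.

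**Independent tests.**
- False difference in either direction: 1 − 0.95^k. For k = 9, 1 − 0.630 = 37.0%. For k = 6, 1 − 0.735 = 26.5%.
- False difference favouring VR, with 0.025 in the favourable tail of each test: 1 − 0.975^k. For k = 9, 1 − 0.796 = 20.4%. For k = 6, 1 − 0.859 = 14.1%.

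**Correlated tests.** With equicorrelated normal statistics and c = 1.96, the rate in either direction is

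1 − ∫ [Φ((c − √ρ·u)/√(1−ρ)) − Φ((−c − √ρ·u)/√(1−ρ))]^k φ(u) du.

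Dropping the second Φ term gives the rate favouring VR.

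| Tests | ρ | Either direction | Favouring VR |
|---|---|---|---|
| 1 | – | 5.0% | 2.5% |
| 6 | 0 | 26.5% | 14.1% |
| 6 | 0.5 | 20.7% | 10.4% |
| 9 | 0 | 37.0% | 20.4% |
| 9 | 0.5 | 26.9% | 13.5% |

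Against the 2.5% favourable tail of one test, the nine-test figures are 13.5/2.5 = 5.4 to 20.4/2.5 = 8.2 times larger. The six-test figures are 10.4/2.5 = 4.2 to 14.1/2.5 = 5.6 times larger. At ρ = 0.9 the nine-test rates fall to 12.4% and 6.2%, still more than double the single-test rates.

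**Scored outcomes only.** Cutting the list to the scored outcomes does not by itself restore 5%. Two independent two-sided tests give 1 − 0.95² = 9.75%, three give 14.3% and four give 18.5%. Holm holds the overall rate at or below 5% under any correlation, with first thresholds of 0.05/2 = 0.025, 0.05/3 = 0.0167 and 0.05/4 = 0.0125.

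**The case against.** The strongest reply is that Section 8.0 is loosely worded rather than wrong in intent. Sections 1.0 and 17.0 separate better performance, comprehension and recall from survey results on training experience and satisfaction, and Section 1.0 makes field-exercise adherence the comparison. Read whole, the protocol may never have meant flow or presence scores to stand for performance. That is fair as to intent. But Section 8.0 is the only place where outcomes and analysis are specified, and an analyst following it has no rule that keeps the two kinds of outcome apart.

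Some stronger readings are tempting, and the documents do not support them:

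- A reader might infer that the plan prescribes nine separate unadjusted tests at 5%. It mentions a single t-test and no alpha. One test per instrument is the natural reading, since no composite is defined, but it remains an inference.
- A reader might take 21–37% as the chance of a false benefit for VR. With two-sided 5% tests that range counts errors in either direction, and its lower end needs six tests at correlation 0.5. A false benefit of 37% would need nine independent one-sided 5% tests (23% at correlation 0.5), and the plan does not state one-sided testing.
- A reader might say that only two of the nine can be marked for accuracy. The scoring of the Training Survey is not shown, so this is not established.

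It could also be said that naming one primary outcome would restore 5%. It would for that test, but it would not stop a self-report difference from being reported as performance.

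**Conclusion.** The concern holds in conditional form. The mislabelling rests on the text and the instruments' names, and needs no numerical assumption: most of the nine are self-report scales, yet all are called performance instruments.

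The size of the error does rest on assumptions. With one two-sided 5% test per instrument, at least one false difference in either direction has probability 37% for nine independent tests and 27% at correlation 0.5 (26% and 21% for six tests). At least one falsely favouring VR has probability about 20% and 13.5% (14% and 10% for six), against 2.5% for a single test. Alpha, sidedness, correlation and the number of instruments comparable between arms are all unstated.

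These figures also take each t-test to have its nominal size. Courses are the randomised unit, so a trainee-level test that ignores clustering would inflate every test. That is a separate matter and is not counted here.

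**What to change.** Before outcome data are seen, divide the Section 8.0 list into two groups.

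(a) **Scored knowledge and skill outcomes:** the Course Workbook, the Toxic Properties Activity, and the field-exercise protocol adherence that Section 1.0 names as the comparison. Only these can support a claim that the modules enhance performance. Test them with Holm at an overall two-sided 5%. The Training Survey joins this group only if it is scored for correctness, and the plan should say whether it is.

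(b) **Self-report scales:** report these as training-experience outcomes, with estimates and 95% intervals and no performance claim. Remove the accuracy and performance labels for this group wherever the list appears, and state which scales are collected in both arms.

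This needs no extra participants. It is mainly rewording of Section 8.0, plus a statement of how field-exercise adherence is scored, since that outcome is missing from the present list. The statistical cost is a first Holm threshold of 0.025, 0.0167 or 0.0125 for two, three or four scored outcomes instead of 0.05. Bonferroni over all nine (0.05/9 = 0.0056 per test) would also control the error, but it costs more and leaves the self-report scales counting as performance.
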